5.2 SAFETY PARAMETERS AND DEFINITIONS

Safety assessments will consist of monitoring and recording adverse events, including serious adverse events and adverse events of special interest, performing protocol-specified safety laboratory assessments, measuring protocol-specified vital signs, and conducting other protocol-specified tests that are deemed critical to the safety evaluation of the study.

Certain types of events require immediate reporting to the Sponsor, as outlined in Section 5.4.

5.2.1 Adverse Events

According to the ICH guideline for Good Clinical Practice, an adverse event is any untoward medical occurrence in a clinical investigation subject administered a pharmaceutical product, regardless of causal attribution. An adverse event can therefore be any of the following:

- Any unfavorable and unintended sign (including an abnormal laboratory finding), symptom, or disease temporally associated with the use of a medicinal product, whether or not considered related to the medicinal product
- Any new disease or exacerbation of an existing disease (a worsening in the character, frequency, or severity of a known condition), except as described in Section [5.3.5.10](#)
- Recurrence of an intermittent medical condition (e.g., headache) not present at baseline
- Any deterioration in a laboratory value or other clinical test (e.g., ECG, X-ray) that is associated with symptoms or leads to a change in study treatment or concomitant treatment or discontinuation from study drug
- Adverse events that are related to a protocol-mandated intervention, including those that occur prior to assignment of study treatment (e.g., screening invasive procedures such as biopsies)

5.2.2 Serious Adverse Events (Immediately Reportable to the Sponsor)

A serious adverse event is any adverse event that meets any of the following criteria:

- Is fatal (i.e., the adverse event actually causes or leads to death)
- Is life threatening (i.e., the adverse event, in the view of the investigator, places the patient at immediate risk of death)

This does not include any adverse event that had it occurred in a more severe form or was allowed to continue might have caused death.

- Requires or prolongs inpatient hospitalization (see Section [5.3.5.11](#))
- Results in persistent or significant disability/incapacity (i.e., the adverse event results in substantial disruption of the patient's ability to conduct normal life functions)
- Is a congenital anomaly/birth defect in a neonate/infant born to a mother exposed to study drug
- Is a significant medical event in the investigator's judgment (e.g., may jeopardize the patient or may require medical/surgical intervention to prevent one of the outcomes listed above)

The terms "severe" and "serious" are not synonymous. Severity refers to the intensity of an adverse event (e.g., rated as mild, moderate, or severe, or according to NCI CTCAE;

see Section 5.3.3); the event itself may be of relatively minor medical significance (such as severe headache without any further findings).

Severity and seriousness need to be independently assessed for each adverse event recorded on the eCRF.

Serious adverse events are required to be reported by the investigator to the Sponsor immediately (i.e., no more than 24 hours after learning of the event; see Section 5.4 for reporting instructions).

5.2.3 Adverse Events of Special Interest (Immediately Reportable to the Sponsor)

Adverse events of special interest are required to be reported by the investigator to the Sponsor immediately (i.e., no more than 24 hours after learning of the event; see Section 5.4 for reporting instructions). Adverse events of special interest for this study include the following:

- Suspected transmission of an infectious agent by the study drug, as defined below
Any organism, virus, or infectious particle (e.g., prion protein transmitting transmissible spongiform encephalopathy), pathogenic or non-pathogenic, is considered an infectious agent. A transmission of an infectious agent may be suspected from clinical symptoms or laboratory findings that indicate an infection in a patient exposed to a medicinal product. This term applies only when a contamination of the study drug is suspected.
- Pneumonitis
- Colitis
- Endocrinopathies: diabetes mellitus, pancreatitis, adrenal insufficiency, or thyroid disease
- Systemic lupus erythematosus
- Neurologic: Guillain-Barré syndrome, myasthenia gravis, meningoencephalitis
- Nephritis
- Events suggestive of hypersensitivity, cytokine release, influenza-like illness, systemic inflammatory response system, or infusion-reaction syndromes
- Retinal vein occlusion
- Serous retinopathy, including events of retinal detachment, retinal pigment epithelium detachment, neurosensory retinal detachment, and central serous chorioretinopathy
- Rhabdomyolysis or Grade ≥ 3 CPK elevation
- Grade ≥ 3 hemorrhage or any grade cerebral hemorrhage
- Grade ≥ 3 rash

- Grade ≥ 3 diarrhea
- Significant liver toxicity
 - AST and/or ALT $> 10 \times$ ULN
 - Cases of potential drug-induced liver injury that include an elevated ALT or AST in combination with either an elevated bilirubin or clinical jaundice, as defined by Hy's law (see Section 5.3.5.7):
 - Treatment emergent ALT or AST $> 3 \times$ ULN in combination with either an elevated total bilirubin ($> 2 \times$ ULN) or clinical jaundice, without initial findings of cholestasis (elevated serum alkaline phosphatase)
 - No other reason can be found to explain the combination of increased ALT/AST and total bilirubin, such as: liver metastasis; viral hepatitis A, B, or C; alcoholic and autoimmune hepatitis; other liver diseases; or exposure to other drugs known to cause liver injury
- Symptomatic heart failure or Grade ≥ 3 left ventricular ejection fraction reduction

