- Guidelines for managing patients who experience atezolizumab-associated adverse events have been revised to include guidelines for hypophysitis and myocarditis and have been provided in an appendix so there is no longer a need to consult the Atezolizumab Investigator's Brochure for management guidelines (Appendix 9). The list of risks was updated in Section 5.1.2 and cross-references have been updated (Sections 1.4.2.2, 4.3.2.2, 5.1.2, 5.1.4.2, 5.1.4.3, 5.1.4.4, and Appendix 3).

Additional minor changes have been made to improve clarity and consistency.

Substantive new information appears in italics. This amendment represents cumulative changes to the original protocol.

PROTOCOL AMENDMENT, VERSION 5: SUMMARY OF CHANGES

PROTOCOL SYNOPSIS

The protocol synopsis has been updated to reflect the changes to the protocol, where applicable.

SECTION 1.4.2.2: Ongoing Clinical Studies Immune-Mediated Adverse Events

Refer to the atezolizumab Investigator's Brochure *and Appendix 9* for details regarding immune-mediated adverse events and identified risks (adverse drug reactions) observed in patients treated with atezolizumab as well as recommended management guidelines for atezolizumab-specific immune-mediated adverse events.

SECTION 3.2: END OF STUDY AND LENGTH OF STUDY

The OS final analysis will be conducted when there are approximately *235 deaths in the study*. ~~178 deaths for the comparison of Arm A versus Arm C and approximately 127 deaths for the comparison of Arm B versus Arm C.~~ This is expected to occur approximately ~~24~~23 months after the first patient is randomized.

SECTION 4.3.2.2: Atezolizumab

Dose modifications to atezolizumab are not permitted. Guidelines for treatment interruption or discontinuation and the management of specific adverse events associated with cobimetinib and atezolizumab are provided in Section 5.1.4 and Appendix 3. For information regarding management of atezolizumab-associated adverse events, please refer to ~~the atezolizumab Investigator's~~ *Appendix 9*.

SECTION 4.5.7.1: Archival and Fresh Tumor Sample for Screening

Extended RAS mutation is defined as mutations occurring in KRAS and NRAS gene codons 12 and 13 of exon 2; 59 and 61 of exon 3; and 117 and 146 of exon 4 (Allegra et al. 2016). Local RAS testing results will be accepted with a copy of the results and interpretation as part of the screening process with a requirement for central confirmation. ~~by Foundation Medicine NGS-based genomic profiling.~~

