5.1.2 Risks Associated with Atezolizumab

Atezolizumab has been associated with risks such as IRRs and immune-related hepatitis, pneumonitis, colitis, pancreatitis, diabetes mellitus, hypothyroidism, hyperthyroidism, adrenal insufficiency, Guillain-Barré syndrome, myasthenic syndrome or myasthenia gravis, meningoencephalitis, *myocarditis*, and *hypophysitis*. In addition, systemic immune activation is a potential risk associated with atezolizumab. Refer to Section 6 of the Atezolizumab Investigator's Brochure for a detailed description of anticipated safety risks for atezolizumab and [Appendix 9](#).

Systemic immune activation is a rare condition characterized by an excessive immune response. Given the mechanism of action of atezolizumab, systemic immune activation is a potential risk when administered in combination with other immunomodulating agents. Systemic immune activation should be included in the differential diagnosis for patients who, in the absence of an alternative etiology, develop a sepsis-like syndrome after administration of atezolizumab, and the initial evaluation should include the following:

- CBC with peripheral smear
- PT, PTT, fibrinogen, and D-dimer
- Ferritin
- Triglycerides
- AST, ALT, and total bilirubin
- LDH
- Complete neurologic and abdominal examination (assess for hepatosplenomegaly)

If systemic immune activation is still suspected after the initial evaluation, contact the Medical Monitor for additional recommendations.

5.1.3 **Risks Associated with Regorafenib**

The overall safety profile of regorafenib is based on data from more than 1200 treated patients in clinical trials including placebo-controlled Phase III data for 500 patients with metastatic colorectal cancer and 132 patients with gastrointestinal stromal tumors. The most serious adverse drug reactions in patients who receive regorafenib are severe liver injury, hemorrhage, hypertension, dermatologic toxicity, cardiac ischemia and infarction, reversible posterior leukoencephalopathy, and gastrointestinal perforation. The most frequently observed adverse drug reactions ($\geq 30\%$) in patients who receive regorafenib are asthenia/fatigue, hand foot skin reaction, diarrhea, decreased appetite and food intake, hypertension, dysphonia and infection.

Please refer to the Stivarga (regorafenib) Prescribing Information for complete information regarding clinical safety.

5.1.4 **Management of Patients Who Experience Specific Adverse Events**

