5.3.1 Adverse Event Reporting Period

Investigators will seek information on adverse events at each patient contact. All adverse events, whether reported by the patient or noted by study personnel, will be recorded in the patient's medical record and on the Adverse Event eCRF.

After informed consent has been obtained **but prior to initiation of study drug**, only serious adverse events caused by a protocol-mandated intervention (e.g., invasive procedures such as biopsies, discontinuation of medications) should be reported (see Section 5.4.2 for instructions for reporting serious adverse events).

After initiation of study drug, all *serious adverse events and Adverse Events of Special Interest, regardless of relationship to study drug, will be reported until 90 days after the last dose of study drug or initiation of new anti-cancer therapy, whichever occurs first. All other adverse events, regardless of relationship to study drug, will be reported until 30 days after the last dose of study drug or initiation of new anti-cancer*

therapy, whichever occurs first. Instructions for reporting adverse events that occur after the adverse event reporting period are provided in Section 5.6.

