Hypophysitis (pan-hypopituitarism), Grade 2 or 3	
 • Withhold atezolizumab for up to 12 weeks after event onset. ^a • Refer patient to endocrinologist. • Perform brain MRI (pituitary protocol). • Initiate treatment with 1–2 mg/kg/day IV methylprednisolone or equivalent and convert to 1–2 mg/kg/day oral prednisone or equivalent upon improvement. • Initiate hormone replacement if clinically indicated. • If event resolves to Grade 1 or better, resume atezolizumab. ^b • If event does not resolve to Grade 1 or better while withholding atezolizumab, permanently discontinue atezolizumab and contact Medical Monitor. ^c • For recurrent hypophysitis, treat as a Grade 4 event.
Hypophysitis (pan-hypopituitarism), Grade 4	
 • Permanently discontinue atezolizumab and contact Medical Monitor. ^c • Refer patient to endocrinologist. • Perform brain MRI (pituitary protocol). • Initiate treatment with 1–2 mg/kg/day IV methylprednisolone or equivalent and convert to 1–2 mg/kg/day oral prednisone or equivalent upon improvement. • Initiate hormone replacement if clinically indicated.

MRI = magnetic resonance imaging; TSH = thyroid-stimulating hormone.

^a Atezolizumab may be withheld for a longer period of time (i.e., > 12 weeks after event onset) to allow for corticosteroids (if initiated) to be reduced to ≤10 mg/day oral prednisone or equivalent. The acceptable length of the extended period of time must be agreed upon by the investigator and the Medical Monitor.

^b If corticosteroids have been initiated, they must be tapered over ≥1 month to ≤10 mg/day oral prednisone or equivalent before atezolizumab can be resumed.

^c Resumption of atezolizumab may be considered in patients who are deriving benefit and have fully recovered from the immune-related event. Patients can be re-challenged with atezolizumab only after approval has been documented by both the investigator (or an appropriate delegate) and the Medical Monitor.

OCULAR EVENTS

An ophthalmologist should evaluate visual complaints (e.g., uveitis, retinal events). Management guidelines for ocular events are provided in [Table 5](#).

Appendix 9: Risks Associated with Atezolizumab and Guidelines for Management of Adverse Events Associated with Atezolizumab (cont.)

Table 5 Management Guidelines for Ocular Events

Event	Management

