Immune-related myocarditis has been associated with the administration of atezolizumab. Immune-related myocarditis should be suspected in any patient presenting with signs or symptoms suggestive of myocarditis, including, but not limited to, dyspnea, chest pain, palpitations, fatigue, decreased exercise tolerance, or syncope. Immune-related myocarditis needs to be distinguished from myocarditis resulting from infection (commonly viral, e.g., in a patient who reports a recent history of gastrointestinal illness), ischemic events, underlying arrhythmias, exacerbation of preexisting cardiac conditions, or progression of malignancy.

All patients with possible myocarditis should be urgently evaluated by performing cardiac enzyme assessment, an ECG, a chest X-ray, an echocardiogram, and a cardiac MRI as appropriate per institutional guidelines. A cardiologist should be consulted. An endomyocardial biopsy may be considered to enable a definitive diagnosis and appropriate treatment, if clinically indicated.

Patients with signs and symptoms of myocarditis, in the absence of an identified alternate etiology, should be treated according to the guidelines in [Table 6](#).

Appendix 9: Risks Associated with Atezolizumab and Guidelines for Management of Adverse Events Associated with Atezolizumab (cont.)

Table 6 Management Guidelines for Immune-Related Myocarditis

Event	Management
Immune-related myocarditis, Grade 1	
 • Refer patient to cardiologist. • Initiate treatment as per institutional guidelines.
Immune-related myocarditis, Grade 2	
 • Withhold atezolizumab for up to 12 weeks after event onset ^a and contact Medical Monitor. • Refer patient to cardiologist. • Initiate treatment as per institutional guidelines and consider antiarrhythmic drugs, temporary pacemaker, ECMO, or VAD as appropriate. • Consider treatment with 1–2 mg/kg/day IV methylprednisolone or equivalent and convert to 1–2 mg/kg/day oral prednisone or equivalent upon improvement.^a • If event resolves to Grade 1 or better, resume atezolizumab. ^b • If event does not resolve to Grade 1 or better while withholding atezolizumab, permanently discontinue atezolizumab and contact Medical Monitor. ^c

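### Version 5 names myocarditis and hypophysitis as atezolizumab risks but leaves both off the AESI list, so a non-serious case that fits no other AESI term misses 24-hour reporting, collection on days 31–90 and the AESI summary

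*Protocol*

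**What the plan says.** The rationale for Version 5 says that the guidelines for atezolizumab adverse events "have been revised to include guidelines for hypophysitis and myocarditis". The list of associated risks in Protocol Section 5.1.2 now ends with "meningoencephalitis, *myocarditis*, and *hypophysitis". Appendix 9, new in this version, says that "Immune-related myocarditis has been associated with the administration of atezolizumab" and gives it a table of its own (Table 6). Its endocrine table (Table 4) has two rows for the pituitary event: "Hypophysitis (pan-hypopituitarism), Grade 2 or 3", and a Grade 4 row.

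Section 5.2.3 lists the AESIs. Its endocrine entry is "Endocrinopathies: diabetes mellitus, pancreatitis, adrenal insufficiency, or thyroid disease", its neurologic entry is "Neurologic: Guillain-Barré syndrome, myasthenia gravis, meningoencephalitis", and its only cardiac entry is "Symptomatic heart failure or Grade ≥ 3 left ventricular ejection fraction reduction". The Version 5 summary of changes shows no edit to this section.

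Three rules depend on AESI status:

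- **Speed.** Section 5.4 puts serious adverse events, AESIs and pregnancies on the 24-hour list, and nothing else.
- **Duration.** Under Section 5.3.1, serious events and AESIs are collected for 90 days after the last dose. Every other event "will be reported until 30 days after the last dose of study drug". Both windows close earlier if new anti-cancer therapy begins.
- **Tabulation.** Protocol Section 6.6 and SAP Section 4.6.2 summarize AESIs as a separate category. The SAP has no AESI list of its own.

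**The concern.** For a non-serious event, AESI status is what brings it to the sponsor quickly and keeps collection open to day 90. It also brings the event under the sponsor's prompt signal evaluation (Section 5.7) and case follow-up (Section 5.5.2), both of which are framed around serious events and AESIs. Two immune-mediated risks were promoted to named status in this version, and the list that controls their reporting did not change. That looks like a missed consequential edit, and no passage gives a reason for leaving them out. At stake is whether late or low-grade cases of two newly recognized risks are seen at all, and whether those that are seen are gathered in the table meant for such events.

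**Working it through.** No design figure is involved, so the check is a comparison of passages with one subtraction.

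**Step 1. Set the Section 5.1.2 risks beside the Section 5.2.3 list.**

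| Risk in 5.1.2 | Counterpart in 5.2.3 |
|---|---|
| Infusion-related reactions | Yes |
| Pneumonitis, colitis | Yes, by name |
| Pancreatitis, diabetes, adrenal insufficiency | Yes, by name |
| Hypo- and hyperthyroidism | Yes, as thyroid disease |
| Guillain-Barré, myasthenia, meningoencephalitis | Yes, by name |
| Hepatitis | Through liver-test thresholds |
| Systemic immune activation (potential risk) | Approximately, through the cytokine-release and systemic-inflammatory entry |
| Myocarditis | Not named |
| Hypophysitis | Not named |

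Only the two additions lack a counterpart.

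**Step 2. Ask whether another entry catches them.** Sometimes. Hypophysitis that shows itself as adrenal insufficiency or thyroid disease meets the endocrine entry. Myocarditis with symptomatic heart failure, or with a fall in ejection fraction of Grade 3 or worse, meets the cardiac entry. But Section 5.3.5.2 tells sites to record a known diagnosis rather than its component signs and symptoms, so a case entered simply as myocarditis or hypophysitis matches no listed term.

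**Step 3. Ask whether non-serious cases are foreseen.** They are. Section 5.2.2 requires severity and seriousness to be judged separately. Appendix 9 has a Grade 1 myocarditis row with no Medical Monitor contact. For Grade 2–3 hypophysitis it asks for that contact only if the event does not resolve while atezolizumab is withheld; recurrences move to the Grade 4 row.

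**Step 4. Follow a case that is non-serious and meets no listed AESI term.**

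- 24-hour report: none required (Section 5.4).
- Collection after last dose: 30 days rather than 90, a difference of 90 − 30 = 60 days. Onset on days 31 to 90 is not collected. The 60 days is a maximum, because new anti-cancer therapy ends either window.
- After the window: Section 5.6 asks for related serious events, and the schedule footnotes in Appendix 1 ask for related serious events or AESIs. This case is neither.
- Tables: if collected, it is in the all-event tables by term, arm and grade, and where applicable in the Grade 3–5 and the interruption or discontinuation tables. It is not in the AESI summary.

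**Step 5. Effect of listing both terms.** The window for such a case goes from 30 to 90 days, and the 24-hour rule and the AESI summary apply. Sample size, power and alpha do not change.

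**The case against.** The strongest reply is that little falls through.

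- **Seriousness.** Hospitalization and the significant-medical-event criterion are broad. The management Appendix 9 contemplates even for Grade 2 myocarditis suggests that many such cases would be classed as serious, and would then have both the 24-hour report and the 90-day window. This largely stands. But the significant-event route rests on the investigator's judgment, and serious cases would still not appear by name in the AESI summary.
- **Sponsor awareness.** Appendix 9 sends Grade 2 and higher myocarditis, Grade 4 hypophysitis and unresolved Grade 2–3 hypophysitis to the Medical Monitor. That stands too, but it sets no 24-hour limit and confers no AESI status.
- **Tables.** Appendix 9 withholds atezolizumab from Grade 2 for both events, so on-treatment cases of that grade should reach the interruption or discontinuation table. The comparison between arms is therefore scattered rather than lost.
- **The lists were never mirrors.** Nephritis and lupus are AESIs but not Section 5.1.2 risks, and no passage requires every associated risk to be an AESI. True, but this gives no reason for omitting the only two named risks with no counterpart. The list is introduced as inclusive, yet nothing in the documents extends it.

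A reader might infer that every non-serious case escapes. Step 2 shows that this is not so. A reader might also size the gap as 60 days across Arms A and B, about 180 + 90 = 270 patients. That is the whole of both arms. Only patients with a non-serious, otherwise unlisted event that begins after day 30 and before any new therapy lose collection. Finally, SAP Section 4.6.2 does not cite Protocol Section 5.2.3. That the list determines the AESI table is a natural inference, since no other list exists, but it is not stated.

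**Conclusion.** The point holds for a defined residual: myocarditis or hypophysitis that is non-serious and meets no other listed AESI term. For that residual the plan as written requires no expedited report, leaves a post-treatment collection gap of up to 60 days, and omits the case from the AESI summary. The documents give no frequency for either event, so the number of patients affected cannot be estimated; given the other routes by which cases are captured, it is likely small. The conclusion assumes that Section 5.2.3 is applied as the operative list and that sites record the diagnosis as instructed. It concerns safety reporting and tabulation only and does not touch the overall survival analysis. It is worth correcting because the risks were added deliberately and the omission is unexplained.

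**What to change.** Reconcile Section 5.2.3 with Section 5.1.2 and Appendix 9 by adding myocarditis and hypophysitis to the AESI list. Add the same two terms to those used for the AESI summary in SAP Section 4.6.2, and have that section point to the protocol list so that the two stay aligned. No dose or management rule changes. The cost is two list entries, the matching search terms and a few more expedited reports.
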